4.2. Extent of Exposure and Concomitant Procedures

4.2.1. Study Drug Exposure

Descriptive statistics for the duration of study drug therapy (IV and oral, and separately for IV therapy and oral therapy) will be summarized by treatment group for the mITT, and Safety populations.

Study drug duration is defined as the

$$\text{date of the last dose of study drug} - \text{first dose of study drug} + 1.$$

The number and percentage of subjects with 1–7, 8-14, 15-28 and >28 days of exposure as defined above will be presented for IV and IV and oral therapy combined. The number and percentage of subjects with 1–3, 4-7, 8-14, 15-28 and >28 days of exposure as defined above will be presented for oral therapy. Descriptive statistics will also be provided separately for the duration of IV therapy and the duration of oral therapy. The number and percentage of subjects switching to oral study drug therapy and a frequency distribution of the day of oral switch will be summarized by treatment group for the Safety and mITT populations.

A by-subject listing of all IV doses over time and a separate by-subject listing of the start and stop dates for oral therapy will be provided.

4.2.2. **Prior and Concomitant Medications**

The number and percentage of subjects who received prior and concomitant medications will be summarized by WHO drug anatomical therapeutic chemical (ATC) classification level 3 and PT.

Medications are considered prior if they are received prior to the first dose of study drug (start date and time [if applicable] is prior to the first dose of study drug) or if the start date is unknown. Medications are considered concomitant if they are received on or after the first dose of study drug (start date and time [if applicable] is on or after the first dose of study drug, stop date and time [if applicable] is after the first dose of study drug), or if the stop date is unknown or continuing. If the stop date is the same as the first dose date of study drug and the stop time is unknown, it will be assumed that the medication stopped prior to the first dose of study drug unless the medication start time is after first dose of study drug time. Date imputations will follow the rules described in [Appendix 8 \(Section 5.8\)](#).

The number and percentage of subjects who receive the following categories of prior and concomitant medications will be summarized by treatment group:

- Systemic antifungal medications received prior to the first dose of study drug (mITT population)
- Systemic antifungal medications (excluding study drug) received on/after the first dose of study drug through the Follow-up visit (mITT population)
- Non-antifungal medications received prior to the first dose of study drug (Safety population)
- Non-antifungal medications received on/after the first dose of study drug through the Follow-up visit (Safety population).

By-subject listings for non-antifungal medications and antifungal medications received prior to the first dose or administered after the first dose of study drug through the FU visit will be provided separately for the Safety population.

4.2.3. **Concomitant Procedures**

Concomitant procedures will be summarized by treatment group, SOC, and PT using the latest version of MedDRA in the mITT population. If the same procedure (based on PT) is reported for the same subject more than once, the procedure is counted only once for that PT. Procedures are considered concomitant if they are performed on or after the first dose of study drug (start date and time [if applicable] is on or after the first dose of study drug, stop date and time [if applicable] is after the first dose of study drug), or if the stop date is unknown or continuing.

A by-subject listing will display procedures on/after the first dose of study drug through the FU visit and will include the verbatim description of the procedure, MedDRA PT, reason for the procedure, and date and time of the procedure.

By-subject listings for transfusions and hemodialysis received prior to the first dose or after the first dose of study drug through the FU visit will be provided separately for the Safety population.

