In this double-blind, double-dummy, active comparator study, two placebo regimens are required; one for subjects randomized to Rezafungin for Injection and one for subjects randomized to caspofungin. In addition, because subjects in the caspofungin arm may be switched to oral step-down therapy, an oral placebo is required for subjects in the Rezafungin for Injection arm. Thus, placebo requirements for each treatment assignment are as follows:

Treatment Assignment	Placebo
Rezafungin for Injection	Placebo for caspofungin IV Placebo for oral step-down therapy (fluconazole)
Caspofungin IV	Placebo for Rezafungin for Injection

In more detail, placebo regimens for each treatment assignment are as follows:

Placebo Regimen for Rezafungin for Injection Treatment Assignment

Subjects will receive a caspofungin IV equivalent regimen of daily placebo IV infusion in a blinded manner. Because subjects randomized to caspofungin may be switched to fluconazole oral step-down therapy, a fluconazole-equivalent regimen of daily oral placebo will be administered for subjects randomized to Rezafungin for Injection at that time.

Placebo Regimen for Caspofungin IV Treatment Assignment

Subjects who are switched to fluconazole oral step-down therapy will receive a Rezafungin for Injection equivalent regimen of weekly placebo IV infusion in a blinded manner.

Duration of Treatment:

The treatment period for study drug administration is ≥ 14 days to ≤ 28 days with the last required dose of study drug on Day 14 and the last possible dose of study drug on Day 28. Treatment may be stopped on any day between Day 14 and Day 28 at the discretion of the Investigator.

Known and Potential Risks

Known Risks

Infusion reactions characterized by flushing, shortness of breath, and nausea have been observed with rezafungin and are similar to infusion reactions noted with other echinocandins. Symptoms of the infusion reaction may resolve without intervention or with either slowing of the infusion rate or interruption of the infusion.

Mild photosensitivity to ultraviolet (UV) light has been demonstrated in subjects administered rezafungin in a Phase 1 clinical trial. Subjects should use measures to reduce sun and other UV light exposure while on study drug, and for 5 half-lives (approximately 30 days) after the last dose of rezafungin administered.

The Investigator’s Brochure should be referenced for additional details or updated information throughout the conduct of the study.

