6.1.2 Subjects Randomized to Caspofungin

Subjects randomized to caspofungin will receive a total treatment of ≥ 14 days beginning with a single caspofungin 70 mg IV loading dose on Day 1, followed by caspofungin 50 mg IV once daily with the option to continue treatment ≤ 28 days. After ≥ 3 days (or the minimum duration of IV therapy advised by the site's national/regional/local guidelines, whichever is greater) of caspofungin treatment, subjects who meet the oral step-down therapy eligibility criteria (see [Section 8.2.3.3](#)) may be switched to oral fluconazole at a dose of 6 mg/kg administered once daily (rounded to the nearest 200 mg increment) with a maximum daily dose of 800 mg (e.g., a subject weighing 73 kg would receive fluconazole 400 mg dose [2 capsules of 200 mg each] based on a 6 mg/kg target dose [$73 \text{ kg} \times 6 \text{ mg/kg} = 438 \text{ mg}$]). NOTE: Refer to dosing section for alternative regimens of fluconazole in subjects with renal impairment in [Section 8.2.3.5](#)). To maintain the blind, subjects in the caspofungin treatment group who have switched to oral step-down therapy will receive matching IV placebo for Rezafungin for Injection once weekly on the days of scheduled Rezafungin for Injection doses until study drug is stopped (Day 8; Day 15 [if applicable] and Day 22 [if applicable]) (see [Figure 1](#) and [Figure 2](#)).

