9.2.6 Day 8 (±1 day)

- One blood sample for PK will be collected predose (≤ 30 minutes prior to the start of the infusion). Draw blood for PK analysis from the OPPOSITE arm or through an arterial line during the infusion; after the infusion is complete, opposite arm or arterial line draws are preferred. For subjects receiving hemodialysis, an attempt should be made to obtain PK samples directly following hemodialysis if still within the required time window.
- Administer study drug:

- IV infusion of study drug over 60 (± 10) minutes (refer to [Section 8.0](#) and the Study Pharmacy Manual for additional infusion rate guidance). Administration should occur 24 (± 2) hours after study drug was administered on the previous day.

OR

- IV infusion of study drug over 60 (± 10) minutes (refer to [Section 8.0](#) and the Study Pharmacy Manual for additional infusion rate guidance). Administration should occur 24 (± 2) hours after study drug was administered on the previous day PLUS oral step-down therapy, if already stepped down.
- Clinical Assessments:
 - A focused physical exam (including a neurological exam) should be performed as clinically indicated by AE screening and course of the underlying disease.
 - Measure vital signs (temperature and the method used [oral, rectal, temporal, tympanic, or core], heart rate, blood pressure, and respiratory rate). Axillary temperatures are allowed, but not preferred.
 - The retinal examination should be repeated in subjects who were negative at baseline if the subject develops visual signs or symptoms of a *Candida* eye infection during the study. Additionally, any neutropenic subjects who recover their neutrophil counts during the study should have an additional retinal examination. Subjects who were negative at baseline and are diagnosed with a *Candida* eye infection after initiating study drug must discontinue study drug (see [Section 7.4.2](#)) but may continue in the study at the Investigator's discretion; all subsequent antifungal drugs, interventions, and outcomes for endophthalmitis or chorioretinitis will be recorded.
- Laboratory Assessments:
 - Draw blood for hematology and serum chemistry tests (see [Appendix 3](#)); for subjects having routine daily blood draws for hematology and serum chemistry as standard of care, values to be entered into the eCRF with generally be the first draw of the day.

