1.2. Synopsis of Study Design

This is a Phase 3, multicenter, prospective, randomized, double-blind, efficacy and safety study of intravenous (IV) Rezafungin for Injection (laboratory code: CD101) versus an active comparator regimen of caspofungin (IV) followed by optional oral fluconazole step-down therapy in subjects with candidemia and/or invasive candidiasis (IC). Subjects will receive either IV Rezafungin for Injection or IV caspofungin, randomized in a 1:1 ratio. Subjects can be switched to oral step-down treatment by the Investigator after ≥ 3 days of IV treatment (or the minimum duration of IV therapy advised by the site's national/regional/local guidelines, whichever is greater) if they meet the oral step-down therapy criteria (as described in the Protocol Section 8.2.3.2).

Subjects randomized to receive Rezafungin for Injection:

Subjects will receive a loading dose of Rezafungin for Injection 400 milligram (mg) in Week 1, followed by 200 mg once weekly for a total of 2 to 4 doses. To maintain the blind, subjects will also receive placebo for caspofungin IV, which will be administered on Days 2-7, Days 9-14 and during the optional dosing period on Days 16-21 and Days 23-28, or will receive daily placebo for oral step-down therapy (first eligibility on Day 4 or later as advised by a site's national/regional/local guidelines), which will be administered every day including rezafungin infusion days.

Subjects randomized to caspofungin:

Subjects will receive a total treatment of ≥ 14 days beginning with a single caspofungin 70 mg IV loading dose on Day 1 followed by caspofungin 50 mg IV once daily with the option to continue treatment ≤ 28 days. After ≥ 3 days (or the minimum duration of IV therapy advised by the site's national/regional/local guidelines, whichever is greater) of caspofungin treatment, subjects who meet the step-down therapy eligibility criteria may

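### SAP 4.2.1 measures IV exposure as a first-to-last-dose span with no placebo or gap rule, so weekly placebo infusions after oral step-down inflate IV duration in the caspofungin arm

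*SAP*

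**What the plan says.** SAP 4.2.1 (Study Drug Exposure) gives one formula. "Study drug duration is defined as the" "date of the last dose of study drug" minus the first dose plus 1. The IV and combined categories (1-7, 8-14, 15-28 and >28 days) use it: "days of exposure as defined above will be presented for IV and IV and oral therapy combined". The oral categories use it too. "Descriptive statistics will also be provided separately for the duration of IV therapy and the duration of oral therapy", with no further definition. The section sets no IV stop date at the oral switch, no rule for gaps between infusions and no exclusion of placebo. Protocol 13.3 plans the same summaries and gives no formula that would override the SAP.

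On dosing, SAP 1.2 states: "Subjects can be switched to oral step-down treatment by the Investigator after ≥ 3 days of IV treatment" (or longer where guidelines require it). Protocol 6.1.2 says that stepped-down caspofungin subjects "will receive matching IV placebo for Rezafungin for Injection once weekly on the days of scheduled Rezafungin for Injection doses", that is, on Day 8 and, if treatment continues, Days 15 and 22. Protocol 8.0 puts a window of ±1 day on each. Protocol 8.2.3.3 allows a return to IV treatment when the subject cannot take oral medication.

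**The concern.** An IV exposure table split by arm is normally read as the amount of IV drug each arm received. In this double-dummy design a span from first to last infusion does not show that for the comparator. Caspofungin stops at the oral switch, but placebo infusions go on once a week, and each later one moves the end of the IV span forward. A subject with a few days of echinocandin can appear to have had two or three weeks.

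In the rezafungin arm the span runs over caspofungin-placebo days, and the number of active doses (2 to 4 planned) is not tabulated. It can be found only in the by-subject listing of IV doses.

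What is at stake is the accuracy of a descriptive table, and whether two programmers given SAP 4.2.1 would report the same IV duration for the same subject.

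**Working it through.** **Inputs**
- Formula: last dose day − first dose day + 1 (SAP 4.2.1).
- Earliest oral dose: Day 4, after caspofungin on Days 1-3 (SAP 1.2; Protocol 8.2.3.2).
- Placebo infusions after step-down: Days 8, 15 and 22, each ±1 day (Protocol 6.1.2 and 8.0).
- Treatment period: at least 14 and at most 28 days, "with the last required dose of study drug on Day 14" (Protocol synopsis, Duration of Treatment).

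**Step 1. Reproduce the plan's own figure.** 14 − 1 + 1 = 14 and 28 − 1 + 1 = 28, which matches the stated treatment period. In the rezafungin arm the match requires placebo to count as study drug. Active infusions alone end on Day 8 or Day 22 and give 8 − 1 + 1 = 8 or 22 − 1 + 1 = 22.

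**Step 2. Does study drug include placebo elsewhere?** Generally, yes.
- Protocol 9.2.6 calls the Day 8 infusion study drug and provides for it "PLUS oral step-down therapy, if already stepped down", without distinguishing arms.
- The step-down criteria in Protocol 8.2.3.3 require at least 3 days of IV study drug in both arms. Rezafungin subjects have active drug on Day 1 only, so placebo infusions must count for them to qualify.
- SAP 4.2.1 itself summarises the switch to oral study drug by arm. In the rezafungin arm that treatment is entirely placebo.

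**Step 3. Apply the formula to a caspofungin subject who takes oral treatment from Day 4.** Caspofungin days: 3 − 1 + 1 = 3, category 1-7.

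| Last placebo infusion | IV duration | With ±1 day | Category at nominal day |
|---|---|---|---|
| Day 8 | 8 − 1 + 1 = 8 | 7-9 | 8-14 |
| Day 15 | 15 − 1 + 1 = 15 | 14-16 | 15-28 |
| Day 22 | 22 − 1 + 1 = 22 | 21-23 | 15-28 |

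At nominal days the ratio to caspofungin days runs from 8/3 = 2.7 to 22/3 = 7.3. Infusions of any kind were given on 3 + 1 = 4, 3 + 2 = 5 or 3 + 3 = 6 days.

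**Step 4. Check that the parts add up.** IV and oral spans overlap, so their sum exceeds the combined duration.

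| Treatment ends | IV | Oral (from Day 4) | Sum | Combined |
|---|---|---|---|---|
| Day 14 | 8 | 14 − 4 + 1 = 11 | 19 | 14 |
| Day 21 | 15 | 21 − 4 + 1 = 18 | 33 | 21 |
| Day 28 | 22 | 28 − 4 + 1 = 25 | 47 | 28 |

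**Step 5. Switch back to IV.** Suppose IV treatment covers Days 1 to a and then Days b to c. The span is c. The days on daily IV treatment number a + (c − b + 1). The difference, b − a − 1, is the number of days on oral treatment, all counted as IV.

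**Step 6. Try the active-drug-only reading.** It gives 3 IV days for this subject. It also reports a complete two-dose rezafungin course as 8 days beside 14 for a caspofungin subject treated to Day 14, so it does not rescue the span formula as a by-arm measure.

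**The case against.** The SAP never says that placebo infusions count as IV therapy. Some wording points the other way: the schedules in both documents have a row naming study drug and placebo as separate items, and SAP 4.1.7 treats the study drug received as rezafungin or caspofungin. This stands as a real ambiguity. It does not supply an exclusion rule, and the usage in Step 2 is the more frequent.

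A reader might infer that the table hides how much of the comparator arm was fluconazole. The documents do not support that. SAP 4.2.1 summarises oral duration separately by arm, and the comparator has no oral placebo, so that table is fluconazole duration. It also tabulates the day of switch by arm. Caspofungin days are the switch day minus 1, apart from missed doses and switch-backs, so a reader can largely recover the true figures.

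A reader might also infer that every stepped-down subject given the Day 8 placebo leaves the 1-7 category. The window rules that out: an infusion on Day 7 with none later gives 7 days. The 7.3-fold figure is an extreme, combining the earliest permitted step-down with treatment to Day 22 or beyond.

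Finally, no test, estimand or population uses this duration, and adverse events are reported as numbers and percentages of subjects rather than exposure-adjusted rates. Counting the days between weekly rezafungin doses is not plainly overcounting either, given the half-life of 127-146 hours in Protocol 4.6. These points stand and limit the matter to reporting.

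**Conclusion.** The point holds for the IV part of the exposure table. As written, SAP 4.2.1 overstates IV duration for caspofungin subjects infused with placebo after the switch. In the Day 4 example the reported figure is about 8, 15 or 22 days (7-9, 14-16 or 21-23 with windows) against 3 days of caspofungin. It also counts oral-only days as IV after a switch back.

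This rests on reading study drug to include blinding placebo, which the documents generally support but the SAP does not state. The number of subjects affected depends on how many step down and when, which the documents do not predict.

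The non-inferiority and superiority analyses, combined IV plus oral duration, fluconazole duration in the comparator and the day-of-switch table are unaffected. Subjects with no infusion after the switch are reported correctly. The wording gives no ground for doubting the efficacy conclusions; it is worth correcting because a stated rule produces a misleading summary and the correction is cheap.

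**What to change.** In SAP 4.2.1:
1. Keep the span formula for IV plus oral therapy combined, and label it *duration of blinded study treatment*.
2. For IV exposure, add by arm the number of active rezafungin infusions (1, 2, 3, 4) and, for the comparator, the number of days on which caspofungin was actually infused, excluding placebo.
3. Apply the existing day categories to caspofungin days only. Rezafungin infusion counts of 1 to 4 would all fall in the 1-7 category and mean nothing there.
4. Leave the oral summary as it is; fluconazole duration is already covered.

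The cost is SAP wording and one extra table. Protocol 8.3 already records the date and completeness of each infusion and the start and end dates of oral treatment, and SAP 4.2.1 lists both by subject. After unblinding, whether an infusion was active follows from arm, scheduled dosing day and whether the subject was on oral treatment. SAP 1.1.1 provides for amendment before database lock and for description in the study report afterwards. No clinical rule changes.

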4.3. Analysis of Efficacy

Unless otherwise stated, all efficacy analyses will be conducted in the mITT population. Subjects will be analyzed in the treatment group to which they were randomized.

By subject listings of the primary and secondary efficacy outcomes will be provided.

4.3.1. Primary Efficacy Analysis

The analysis of the **primary efficacy outcome for the FDA** will be based on the mITT population.

The non-inferiority test will be a one-sided hypothesis test performed at the 2.5% level of significance. This non-inferiority test will be based on the upper limit of the two-sided 95% confidence interval (CI). The primary efficacy outcome is the percentage of subjects that died at Day 30.

The number and percentage of subjects in each treatment group that are alive and deceased (or with missing data) at Day 30 (-2 days) will be tabulated.

The null and alternative hypotheses are as follows:

$$H_0: p_1 - p_2 \geq \Delta, \text{ and}$$

$$H_1: p_1 - p_2 < \Delta,$$

where p_1 is the all-cause mortality rate at Day 30 (-2 days) in the Rezafungin for Injection treatment group, p_2 is the primary ACM at Day 30 (-2 days) rate in the caspofungin treatment group, and Δ is the non-inferiority margin of 20%.

To test the null hypothesis, a two-sided 95% CI for the observed difference in primary outcome rates (Rezafungin for Injection treatment group minus caspofungin treatment group) will be calculated for the mITT population using the unadjusted methodology of Miettinen and Nurminen (Miettinen and Nurminen, 1985). If the upper limit of the 95% CI for the difference in the mITT population is lower than 20%, then the null hypothesis will be rejected and non-inferiority of Rezafungin for Injection versus caspofungin will be declared.

To control the overall alpha level, superiority of rezafungin for ACM at Day 30 will be tested in the following order:

- If NI is declared for ACM at Day 30 in the mITT population and the rate of ACM at Day 30 in the rezafungin treatment group is lower than the caspofungin treatment group, the

difference between the treatment groups will be tested for superiority. If the upper bound of the 95% CI is less than 0, superiority of rezafungin will be concluded.

- For the subgroup of subjects with invasive candidiasis (final diagnosis), a two-sided 95% CI for the observed difference in the rate of ACM at Day 30 will be calculated using the unadjusted methodology of Miettinen and Nurminen. If superiority is declared in the mITT population for ACM at Day 30 and the rate of ACM at Day 30 in the rezafungin treatment group is lower than the caspofungin group for invasive candidiasis subjects, superiority of rezafungin will be tested. If the upper bound of the 95% CI is less than 0, superiority of rezafungin will be concluded.

The analysis of the **primary efficacy outcome for the EMA** will be based on the mITT population. The non-inferiority test will be a one-sided hypothesis test performed at the 2.5% level of significance. This non-inferiority test will be based on the lower limit of the two-sided 95% confidence interval (CI). The primary efficacy outcome is the percentage of subjects that have a global response of cure at Day 14 (± 1 day) as confirmed by the DRC.

The number and percentage of subjects in each treatment group defined as global cure, failure and indeterminate will be tabulated, as will the overall category combining Failure and Indeterminate.

The null and alternative hypotheses are as follows:

$$H_0: p_1 - p_2 \leq -\Delta, \text{ and}$$

$$H_1: p_1 - p_2 > -\Delta,$$

where p_1 is the primary efficacy outcome rate in the Rezafungin for Injection treatment group, p_2 is the primary efficacy outcome rate in the caspofungin treatment group, and Δ is the non-inferiority margin of 20%.

To test the null hypothesis, a two-sided 95% CI for the observed difference in primary outcome rates (Rezafungin for Injection treatment group minus caspofungin treatment group) will be calculated for the mITT population. If the lower limit of the 95% CI for the difference in the mITT population exceeds -20% , then the null hypothesis will be rejected and the non-inferiority of Rezafungin for Injection to caspofungin will be declared.

To control the overall alpha level, superiority of rezafungin for global response will be tested in the following order:

- If NI is declared and the percentage of subjects that have a global response of cure at Day 14 (± 1 day) as confirmed by the DRC in the rezafungin treatment group is higher than the caspofungin treatment group, the difference between the treatment groups will be tested for superiority. If the lower bound of the 95% CI is greater than 0, superiority of rezafungin will be concluded.

- For the subgroup of subjects with invasive candidiasis (final diagnosis), a two-sided 95% CI for the observed difference in global cure at Day 14 for the mITT population will be calculated using the unadjusted methodology of Miettinen and Nurminen. If superiority is declared for the EMA primary efficacy outcome of global response at Day 14 in the mITT population, and the global cure rate in the rezafungin treatment group is higher than the caspofungin group for invasive candidiasis subjects, superiority of rezafungin will be tested. If the lower bound of the 95% CI is greater than 0, superiority of rezafungin will be concluded.

A stratified 95% CI will be determined based on the two randomization strata: diagnosis (candidemia only; invasive candidiasis) and APACHE II score/ANC (APACHE II score ≥ 20 OR ANC < 500 cells/ μ L; APACHE II score < 20 AND ANC ≥ 500 cells/ μ L) at Screening. If there are < 5 subjects within a stratum and treatment group, or there is a 0 count within a stratum for a treatment group the categories will be combined. The 95% CI interval will be computed using the stratified methodology of Miettinen and Nurminen. Cochran-Mantel-Haenszel weights will be used for the stratum weights in the calculation of the CI as follows, where n_{1i} = number of subjects in Rezafungin for Injection treatment group in the i th stratum; n_{2i} = number of subjects in caspofungin treatment in the i th stratum:

$$W_i = \frac{n_{1i}n_{2i}}{n_{1i} + n_{2i}}$$

The reasons for having a global response of failure or indeterminate at Day 14 (± 1 day) will be presented using the number and percentage of subjects displayed by treatment group in the mITT population. Subjects who miss the efficacy assessment due to COVID-19 will have an indeterminate response and the number and percentage of subjects with an indeterminate response due to COVID-19 will be summarized.

Other subgroup analyses, including analyses by the pre-, peri- and post-COVID-19 period, will be conducted for descriptive purposes. Depending on the number of subjects in the study diagnosed with COVID-19, ACM at Day 30 and global response may be analyzed in patients with and without COVID-19.

